7.2.3.1 Data collected from the dysmorphology examination

- Live born infants in all cohorts will be examined by 1 of 5 study dysmorphologists/geneticists. These study-specific health care providers who are performing the dysmorphology examination for minor malformations are highly qualified experts, trained specifically to perform the blinded infant evaluations.
- The physical examination of these infants includes evaluation of both major and minor structural defects, which will provide increased sensitivity for detecting the presence of specific patterns of malformation. All live born infants will be examined, to the best extent possible, within the first year of life. The OTIS registry study staff will group and schedule these follow-up examinations with study families, typically in the participant's home. These are scheduled to meet the study criteria of infant age, to maximize physician blinding as to exposure status, and to minimize travel time and expense.
- Infant examinations will be conducted using a standard checklist of minor malformations included in a standard physical evaluation form. In addition, digital photographs of the infant's face will be taken to aid in validating any diagnoses.
- Dysmorphologists/geneticists will perform these examinations blinded to the exposure or control group status of the mothers. Because subjects with MS may have visible evidence of the disease, the use of a disease-matched control group allows for preservation of physician blinding.
- Data collected from these evaluations include:
 - Presence or absence of 1 or more of ~130 minor structural defects on the standard checklist
 - Presence of any major structural defect
 - Length and head circumference
 - Infant photographs

7.2.3.2 Outcome classification for structural defects for cohort study

The method for classifying structural defects for purpose of analysis has been previously described by the study investigators and the OTIS Research Group and has been used in previous studies conducted by this group, including the current OTIS Autoimmune Diseases in Pregnancy Project (Chambers et al, 2001; Chambers et al, 2010; Centers for Disease Control and Prevention, 1998)(8)(10)(12).

7.2.3.3 Classification of major and minor structural defects

- Definitions: a major structural defect is defined as a defect which occurs in less than 4 percent of the population and which has either cosmetic or functional significance to the child (e.g., a cleft lip). The CDC's MACDP coding manual for major structural defects will be used as a guide for categorization. A minor structural defect is defined as a defect which occurs in less than 4 percent of the population but which has neither cosmetic nor functional significance to the child (e.g., complete 2,3 syndactyly of the toes).
- Time period for identification: structural defects identified up to 1 year of age in the dysmorphological examination or the medical record will be included in the analysis.
- Categorization of defects: Defects identified in pregnancies ending in live birth will be considered in the primary analyses; data will be collected on defects occurring in pregnancies that end in spontaneous abortion, stillbirth and elective termination and these will be considered in secondary analyses.
- All definite and possible major structural defects reported in any study subject are reviewed by the lead study dysmorphologist, for classification and coding. A secondary level of review is provided by the Scientific Advisory Board members with expertise in this area.

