3.2.1 Cohort study potential biases, limitations and strengths

The primary limitation of a cohort study utilizing volunteer subjects is selection bias (Honein et al, 1999)(4). The use of comparably selected controls in both groups will address this concern to some extent. However, women who agree to enroll in the cohort study may represent particularly high or low risk pregnancies. However, the study results will be strictly generalizable to women fitting the profile of the sample of pregnant women who enroll.

Because early prenatal testing is prevalent in the US and Canada, it may be difficult to achieve adequate numbers of patients, if all pregnancies with prior prenatal testing were excluded from the analysis. Therefore, the registry cohort study will include pregnancies, enrolled prior to outcome, but after a prenatal test, as long as the test does not indicate a fetus with a major structural defect. The FDA guidance document, "Guidance for Industry, Establishing Pregnancy Exposure Registries" dated August, 2002(5) acknowledges that such an approach may be necessary to accrue adequate numbers. However, this practice could potentially bias the results by lowering the overall birth prevalence of birth defects among

those with normal prenatal test results. The data analysis will address this by stratifying use of prenatal testing prior to enrollment.

The calculation of frequency of birth defects excludes fetal losses (spontaneous abortions, induced abortions, or fetal deaths) for which no birth defects have been detected as they may introduce a classification bias. It is unknown what percentage of these pregnancies consists of potentially normal outcomes or birth defects. The registry study attempts to obtain information on birth defects detected at the time of the outcome. However, the malformation status of the aborted fetus may not be known.

It is expected that virtually all exposures to teriflunomide will occur in unintended pregnancies. More than half of all pregnancies in the U.S. are unintended, (Henshaw, 1998)(6) and this may lead to age, race, and other biases in the sample. For example, the rate of unintended pregnancies is higher among low-income women/families than among the other socioeconomic groups (Finer & Zolner, 2011)(7). Data on intendedness of pregnancy is collected as part of the study interview from all mothers. These factors will be taken into consideration in the recruitment of comparison groups and in the analysis.

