4.1 PRIMARY OBJECTIVE

To evaluate any potential increase in the risk of major birth defects in the first year of life, in teriflunomide-exposed pregnancies.

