8.3.2 Secondary endpoints

The secondary endpoints of this study include: proportion of major structural defects in all pregnancies excluding lost-to-follow-up, prevalence of a specific pattern of 3 or more minor structural defects in the live born infants who receive the dysmorphological examination, rates of spontaneous abortion, preterm delivery, proportion of live born infants who are small for gestational age (less than or equal to 10th percentile for gestational age and sex) on weight, length or head circumference, and proportion of infants less than or equal to the 10th percentile for sex and age on weight, length or head circumference at 1 year postnatal evaluation. The above endpoints, other than spontaneous abortion and preterm delivery, are binary and will be analyzed in the same fashion as major structural defects, with the exception that the Chi-squared test will be used for comparison between the exposed and the comparison group when the events are not rare. For spontaneous abortion and preterm delivery, survival analyses incorporating left truncation for spontaneous abortion (women may enroll in the study any time between 0 to 20 weeks of gestational age) and right censoring when the subject is no longer at risk of the event are conducted. The comparison between the exposed and the comparison group will be carried out using log-rank test, and confounders will be adjusted using the Cox proportional hazards regression model.

For all endpoints, exposure effect will also be investigated using the timing and dose of exposure, in a fashion similar to using the group indicator as above.

Also influencing fetal exposure is the success of the cholestyramine elimination procedure. Therefore, detailed data on the dose, gestational timing of the elimination procedure (s) and adherence to the guidelines for drug elimination procedure will be incorporated into the analysis of exposure in relation to outcome, and these maternally collected data will be supplemented by medical records and blood levels as available.

CSD-003149 VERSION N°1.0 (20-JUL-2010)

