8.3.3 Pregnancies resulting in multiple births

For the primary endpoint:

- Major Structural Defects: In pregnancies that result in multiple births where one or more multiples are malformed, the pregnancy will be counted as one malformed outcome.

For secondary end points:

- Patterns of Minor Malformations: In pregnancies that result in multiple births where one or more multiples have 3 or more minor malformations all infants will be considered in establishing a pattern but only 1 infant of a multiple will count towards the minimum of 2 to establish the pattern.
- Spontaneous abortion: if all multiples are aborted, the outcome is considered one spontaneous abortion. If one or more fetuses survive to live birth, the outcome is considered live birth, and the spontaneous loss(es) are footnoted in study periodic tables as it is unknown what proportion of multiples result in singleton live births.
- Preterm delivery and Small for Gestational Age (SGA): Multiples are excluded from these analyses as they are at inherent high risk of these outcomes.

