8.4 DETERMINATION OF SAMPLE SIZE

Based on previous experience with the OTIS Autoimmune Diseases in Pregnancy Project, it is estimated that subjects will be an average of 6-9 weeks post-LMP at the time of enrollment. Given this mean gestational timing at enrollment, the anticipated spontaneous abortion and stillbirth rate is 10%, the estimated elective abortion rate is <2%, the estimated lost-to-follow-up rate is 4% (based on previous OTIS experience) resulting in approximately 64 live born infants from a total of 75 enrolled in the teriflunomide-exposed group and 106 live born infants in each comparison group from a total of 125 enrolled in each group at the end of 5 years of recruitment. Experience with the current OTIS Autoimmune Diseases in Pregnancy Project has demonstrated a yield of approximately 90% live born infants from the total proportion enrolled. Therefore, the estimated yield of 85% in this proposal is conservative. We estimate baseline rates of major structural defects, spontaneous abortion, premature delivery, and small for gestational age based on previous OTIS studies and on general population data. With this sample size, at 80% power and 2-sided significance level of 0.05, using Fisher's exact test we will be able to detect a relative risk of 5.57 for proportion of major structural defects in the teriflunomide exposed group versus the diseased matched comparison group, which has an assumed major structural defect rate of 3%, which is the background rate of the external comparison group (MACDP). There is no evidence of an increased risk of major structural defects in general in women with MS. The following table also provides the type of differences that can be detected between the primary comparison groups for a pattern of minor malformation, spontaneous abortion, preterm delivery, and small for gestational age, given the baseline rates assumed in the comparison group, with at

Ensure that the printed copy of this document is the current version available on the Intranet.

least 80% power and 2-sided significance level of 0.05, under the sample size, except as otherwise noted(13).

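### No specified analysis follows Section 3.2.1's own rule for fetal losses: the all-pregnancies secondary keeps losses with no detected defect in its denominator, and the live-birth primary omits confirmed defects in stillbirths and terminations

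*Protocol*

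**What the plan says.** Four parts of the protocol bear on which pregnancies enter the defect proportion.

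- **Objective (4.1):** "To evaluate any potential increase in the risk of major birth defects in the first year of life, in teriflunomide-exposed pregnancies".
- **Bias discussion (3.2.1):** the frequency calculation "excludes fetal losses (spontaneous abortions, induced abortions, or fetal deaths) for which no birth defects have been detected". The reason given is classification bias, since it is unknown how many of these losses were normal. The wording removes losses with no detected defect and by implication leaves in those with one.
- **Primary analysis (7.2.3.3, 8.2, 8.3.1 and the synopsis):** "Defects identified in pregnancies ending in live birth will be considered in the primary analyses". Defects in spontaneous abortions, stillbirths and elective terminations are collected and assigned to secondary analyses.
- **Secondary analysis (8.3.2 and the synopsis):** "proportion of major structural defects in all pregnancies excluding lost-to-follow-up". Section 8.2 lists the same variable as a proportion in all pregnancies.

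On the unit of analysis, Section 8.2 defines the primary as a proportion of live born infants. Section 8.3.3 says that where one or more of a multiple birth is malformed, "the pregnancy will be counted as one malformed outcome".

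**The concern.** Section 3.2.1 states a rule and a reason for it, and neither defined analysis obeys the rule. The primary is narrower, because it drops a loss even when a major defect was confirmed. The secondary is wider, because it keeps losses in which nothing was detected, and a proportion over all pregnancies then treats them as unaffected. That is the classification problem Section 3.2.1 warns about.

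The choice matters because events are few. With 3 of 106 affected in Cohort II, 7 of 64 in Cohort I gives a two-sided Fisher p of 0.042. If one of those seven ends in termination, 6 of 63 gives p = 0.080. A single case leaving the primary can change its result.

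A smaller point concerns units. Section 8.3.3 counts a malformed multiple pregnancy once in the numerator, while Section 8.2 counts infants in the denominator.

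**Working it through.** **Inputs from Section 8.4 and Table 3.** Live births 64 of 75 (Cohort I) and 106 of 125 (Cohort II); baseline defect rate 3%; detectable relative risk (RR) 5.57, so 3% × 5.57 = 16.71% in the exposed; spontaneous abortion and stillbirth 10%, elective abortion under 2%, lost to follow-up 4%, with the same rates used for every cohort; detectable miscarriage RR 2.55 on a 10% baseline. The stated operating point is "at 80% power and 2-sided significance level of 0.05".

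**Step 1. Reproduce the plan's figure.** Exact power of Fisher's test by binomial enumeration:
- two-sided p taken as twice the one-sided tail, 64:106: power 80.9% at RR 5.57, and RR 5.51 at 80% power;
- the same test at an 84% yield (1 − 0.10 − 0.02 − 0.04), 63:105: RR 5.57 at 80% power;
- probability-ordered two-sided p, 64:106: power 84.5% at RR 5.57.

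The stated 5.57 reproduces. The probability-ordered test is used below, so the reference power is 84.5%.

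**Step 2. The all-pregnancies denominator.** If losses carry no detected defect, the observed rate is p × (1 − m), where m is the fraction of followed-up pregnancies ending in such a loss. The RR is therefore multiplied by (1 − m1)/(1 − m2).

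At the protocol's detectable miscarriage effect, m1 = 2.55 × 10% = 25.5% and m2 = 10%. The factor is 0.745/0.90 = 0.83. A true RR of 3 appears as 2.48, and 5.57 as 4.61.

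At the planned rates, followed-up pregnancies are 75 × 0.96 = 72 and 125 × 0.96 = 120, so losses are 72 − 64 = 8 and 120 − 106 = 14. Other loss counts are assumptions.

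| Losses, Cohort I / II | Rates | RR | Power (72:120) |
|---|---|---|---|
| 8 / 14 (planned) | 14.85% vs 2.65% | 5.60 | 84.3% |
| 16 / 14 (assumed) | 13.00% vs 2.65% | 4.90 | 74.0% |
| 20 / 14 (assumed) | 12.07% vs 2.65% | 4.55 | 67.5% |

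**Step 3. The live-birth primary.** If a share t of malformed fetuses ends in termination or loss, the live-birth rate is p(1 − t)/(1 − pt), and about n(1 − pt) live births remain. The protocol gives no value for t, so every row but the first is an assumption.

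| t, Cohort I / II | Rates | Apparent RR | n | Power |
|---|---|---|---|---|
| 0 / 0 | 16.71% vs 3.00% | 5.57 | 64:106 | 84.5% |
| 20% / 10% | 13.83% vs 2.71% | 5.11 | 62:106 | 73% |
| 30% / 10% | 12.31% vs 2.71% | 4.55 | 61:106 | 61% |
| 50% / 20% | 9.12% vs 2.41% | 3.78 | 59:105 | 41% |
| 20% / 20% | 13.83% vs 2.41% | 5.73 | 62:105 | 74.5% |
| 50% / 50% | 9.12% vs 1.52% | 5.99 | 59:104 | 56% |
| 20% / 40% | 13.83% vs 1.82% | 7.59 | 62:105 | 81.5% |

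The RR falls only in the rows where Cohort I loses the larger share. Power falls in every row, including those with equal shares.

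**The case against.** A reader might infer that both analyses necessarily pull a true effect toward the null. The documents do not support that. Section 8.4 plans the same loss rates for every cohort, and under those the all-pregnancies RR stays at about 5.60. With equal shares the live-birth RR rises slightly, and with larger losses in Cohort II it rises further.

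A reader might also infer that severe cases would leave mainly from the exposed cohort. No passage says exposed women are scanned more closely or end affected pregnancies more often. Section 3.2.1 says only that virtually all exposures are expected in unintended pregnancies. That makes a difference plausible but gives no rate. The planned elective abortion rate under 2% means fewer than 1.5 terminations among 75. At RR 5.57 about 64 × 0.1671 = 10.7 fetuses are malformed, so a 30% share is about 3.2 and a 50% share about 5.3. Most of those would have to be stillbirths or other losses, so these rows are upper-range assumptions.

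The live-birth primary has a real defence. It fits the first-year-of-life wording of the objective, and live born infants in all cohorts get a blinded, standardised examination. Losses would enter only when a defect happened to be detected, so unequal prenatal scrutiny could bias that analysis the other way. Defects in losses are also collected, analysed as secondary and reported promptly to the sponsor, so the registry does not lose them. Section 8 is a specification for a later analysis plan.

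All of this stands. It limits the size and direction of the bias and argues against replacing the primary. It does not reconcile Section 3.2.1 with the definitions in Sections 7 and 8.

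**Conclusion.** The inconsistency is established on the text alone: Section 3.2.1 states a rule, and neither the primary nor the all-pregnancies secondary follows it. That the secondary treats unexamined losses as unaffected is a consequence of its denominator; Section 8.3.2 does not say so in words.

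The bias is conditional. The secondary RR is diluted only if losses with no detected defect are more frequent in Cohort I: by 0.83 at the protocol's own detectable miscarriage effect, and hardly at all at the planned rates. The primary RR is attenuated only if affected pregnancies are lost or terminated more often in Cohort I, with 5.57 appearing as 5.11 to 3.78 over the assumed range 20%/10% to 50%/20%. At equal 20% shares the cost is power, from 84.5% to about 75%, and not RR. The stronger conclusion, that the live-birth primary must be replaced, does not follow, because the alternative carries its own ascertainment risk. The mismatch of units is a wording defect whose size the documents do not allow to be calculated.

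**What to change.** In the synopsis and Sections 8.2 and 8.3.2, redefine the all-pregnancies secondary by the Section 3.2.1 rule:

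- **Numerator:** pregnancies with a confirmed major defect, whatever the outcome.
- **Denominator:** pregnancies with at least one live birth, plus losses or terminations in which a defect was detected.
- **Unit:** the pregnancy in both, and in the primary too, so that Sections 8.2 and 8.3.1 agree with 8.3.3.

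Keep the live-birth primary. Report the redefined analysis beside it as the key sensitivity analysis, and state that the primary can be biased toward the null if affected pregnancies are lost more often in Cohort I.

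The cost is wording. Prenatal test results, pathology where relevant and medical records are already collected for all outcomes, and reported major defects are already reviewed and classified. The drawback is that defect detection in losses is incomplete and may differ by cohort, so the two results should be read together.

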7.2.3.4 Outcome classification for secondary endpoints for cohort study

- Pattern of minor structural defects is defined as any 2 or more infants receiving the study dysmorphology examination in the teriflunomide-exposed cohort (Cohort I) who have the same 3 or more minor structural defects. If a pattern or patterns are identified, the prevalence of the same pattern in Cohorts II and III is evaluated.
- Spontaneous abortion: spontaneous abortion is defined as non-deliberate fetal death which occurs prior to 20 completed week's post-LMP.
- Elective abortion: elective abortion is defined as deliberate termination of pregnancy at any time in gestation.
- Stillbirth: stillbirth is defined as non-deliberate fetal death anytime in gestation at or after 20 completed week's post-LMP.
- Premature delivery: premature delivery is defined as live birth prior to 37 completed weeks gestation as counted from LMP (or calculated from first-trimester ultrasound-derived due date if last menstrual period uncertain or more than 1 week discrepant).

CSD-003149 VERSION N°1.0 (20-JUL-2010)

Ensure that the printed copy of this document is the current version available on the Intranet.

Elective cesarean deliveries or inductions prior to 37 completed weeks will be considered separately.

- Small for gestational age: small for gestational age is defined as birth size (weight, length or head circumference) less than or equal to the 10th percentile for sex and gestational age using National Center for Health Statistic (NCHS) pediatric growth curves for full term infants. Prenatal growth curves will be used for premature infants.
- Postnatal growth deficiency up to 1 year of age: postnatal growth deficiency is defined as postnatal size (weight, length or head circumference) less than or equal to the 10th percentile for sex and age using NCHS pediatric growth curves, and adjusted postnatal age for premature infants.
- Lost-to-follow-up: Subjects will be considered lost-to-follow-up if they have completed the initial intake interview but subsequently fail to complete the outcome interview and medical records release despite a standard number of telephone attempts and attempt to contact by mail as per study procedure manual within 1 year of the mother's estimated due date. Voluntary subject withdrawals will be considered separately.

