4.2 SECONDARY OBJECTIVES

To evaluate the potential effect of teriflunomide exposure on other adverse pregnancy outcomes including any potential pattern of minor birth defects, spontaneous abortion, stillbirth, preterm delivery, small for gestational age at birth and at 1 year follow-up.

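### SGA is defined as a gestational-age percentile, but the reference named for full-term births is the pediatric curves that the protocol elsewhere reads by age, so term births appear to share one cut-off per sex

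*Protocol*

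**What the plan says.** Section 4.2 makes "small for gestational age at birth and at 1 year follow-up" a secondary objective. Section 7.2.3.4 gives the working definitions:

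- **Size at birth, full-term infants:** any of three measurements (head circumference, length, weight) with a value "less than or equal to the 10th percentile for sex and gestational age using National Center for Health Statistic (NCHS) pediatric growth curves".
- **Size at birth, preterm infants:** "Prenatal growth curves will be used for premature infants".
- **Size up to 1 year:** "less than or equal to the 10th percentile for sex and age using NCHS pediatric growth curves, and adjusted postnatal age for premature infants".
- **Where preterm ends:** "premature delivery is defined as live birth prior to 37 completed weeks gestation as counted from LMP", with a first-trimester ultrasound due date as the fallback for dating.

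Section 8.3.2 restates the birth endpoint as the "proportion of live born infants who are small for gestational age (less than or equal to 10th percentile for gestational age and sex"). Section 8.3.3 removes multiples from the SGA analysis. Table 3 in section 8.4 assumes a 10% SGA rate and a 6% premature delivery rate in Cohort II.

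**The concern.** A percentile for gestational age needs a reference with a gestational-age axis. Section 7.2.3.4 assigns such a reference, the prenatal curves, only to births before 37 weeks. For all later births it names curves that its own next bullet enters by sex and age after birth. At delivery every full-term infant has postnatal age zero, so on that reading the curves give one value per sex and a 37-week infant is held to the same threshold as a 41-week infant.

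Two things are at stake. First, the percentile promised in sections 7.2.3.4 and 8.3.2 is not delivered for most births. With 6% preterm in Table 3, about 94% of live births (0.94 × 106 ≈ 100 in Cohort II) would be scored without a week-specific reference. Second, SGA becomes partly a measure of when the infant was born. If cohorts differ in timing of delivery within term, an SGA contrast can appear with no difference in fetal growth. The potential confounders listed in section 8.2 include gestational age at enrollment but not at delivery. That list is open-ended, but nothing stated in it corrects the problem.

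**Working it through.** **1. The plan's own SGA figure.** Table 3 gives 64:106, a 10% baseline, a detectable relative risk (RR) of 2.68 and a chi-square test; section 8.4 gives two-sided 0.05 and 80% power.

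- p1 = 0.268, p2 = 0.10, pooled p = (64 × 0.268 + 106 × 0.10)/170 = 0.1632.
- Null SE = √[0.1632 × 0.8368 × (1/64 + 1/106)] = 0.0585.
- Alternative SE = √[0.268 × 0.732/64 + 0.10 × 0.90/106] = 0.0626.
- z = (0.168 − 1.96 × 0.0585)/0.0626 = 0.852, so power is 80.3%. Exactly 80% is reached at RR 2.67.

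The stated figure reproduces. The point concerns the definition of the endpoint, not this calculation.

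**2. The definitions side by side.**

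| Outcome | Infants | Reference named | Read by |
|---|---|---|---|
| SGA at birth | full-term | NCHS pediatric curves | sex and gestational age (as worded) |
| SGA at birth | premature | prenatal curves | not stated further |
| Growth to 1 year | all | NCHS pediatric curves | sex and age, corrected for prematurity |

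The first and third rows use the same curves with different axes. The separate prenatal reference for preterm births suggests that the pediatric curves carry no gestational axis.

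**3. What one cut-off does (illustration).** The documents give no birth size by week, so every input here is an assumption: normal birth weight, SD 430 g; mean rising by g = 100 to 160 g per week; term births at weeks 37/38/39/40/41 of 10/20/32/28/10%; one cut-off c placed so that 10% of all term births fall below it. The mean at 39.5 weeks is set at 3,450 g; this value cancels out.

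Share called SGA at week w = Φ[(c − mean at w)/430].

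- g = 100: c = 2,838 g. Week 37: (2,838 − 3,200)/430 = −0.842, so 20.0%. Week 41: (2,838 − 3,600)/430 = −1.772, so 3.8%.
- g = 160: c = 2,784 g. Week 37: (2,784 − 3,050)/430 = −0.619, so 26.8%. Week 41: (2,784 − 3,690)/430 = −2.107, so 1.8%.

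| Week | g = 100 | g = 160 | Week-specific reference |
|---|---|---|---|
| 37 | 20.0% | 26.8% | 10% |
| 38 | 14.1% | 16.1% | 10% |
| 39 | 9.6% | 8.6% | 10% |
| 40 | 6.2% | 4.1% | 10% |
| 41 | 3.8% | 1.8% | 10% |

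The direction holds for any positive weekly gain.

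**4. Effect on a comparison.** Suppose one cohort has s more of its term births at weeks 37 to 38 (split equally), taken proportionally from weeks 39 to 41, and no growth effect. Its SGA rate is 0.10 + s × (mean rate at 37–38 − mean rate at 39–41).

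- g = 100: 0.1706 − 0.0739 = 0.0967. With s = 0.10 the rate is 10.97% (RR 1.10); with s = 0.20 it is 11.93% (RR 1.19).
- g = 160: 0.2145 − 0.0586 = 0.1559. With s = 0.10 the rate is 11.56% (RR 1.16); with s = 0.20 it is 13.12% (RR 1.31).

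With s = 0 the RR is 1, and only misclassification remains.

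**5. Chance that such an artefact is declared significant.** Exact rejection probability of the uncorrected chi-square test at 64:106 with a 10% baseline: 4.7% at RR 1.0, 5.5% at RR 1.1, 10.0% at RR 1.31.

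**The case against.** The best reply is that the SGA bullet does say gestational age, and section 8.3.2 says it again, so the target is right. The curves are not reproduced and none of the protocol's references is an NCHS chart. That they have no gestational axis is inferred from a neighbouring bullet on a different outcome. This stands as a limit: the inference is strong, because prenatal curves are reserved for preterm births, but it is an inference.

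A reader might go further and conclude that SGA will be biased against the exposed cohort, for example because women with MS have more planned early-term deliveries. The documents do not support this. No such mechanism appears in them, and section 3.1 describes pregnancy course and birth outcomes in MS as generally similar to those without it. The primary comparison for SGA (section 8.2.2) is between two MS cohorts, where an effect of MS itself would largely cancel. Equal delivery timing is not guaranteed either: section 8.3.1 says that the cohorts are not matched on severity.

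A reader might also put the over-calling much higher. An SD of 450 g with 37-week infants 300 to 500 g below the term mean gives 27% to 43%. Those inputs are not in the documents, and the milder assumptions above give 20% to 27%. All these figures model weight alone, whereas the endpoint is weight, length or head circumference. Over-calling early in term is also offset within a cohort by under-calling later.

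Finally, the spurious RR is small beside the 2.68 that the study is sized to detect, and step 5 shows that a false significant result would be uncommon. That is fair, though the estimate would still shift. The exact chart edition can be left to the analysis plan. The choice of pediatric curves for term births cannot, because the protocol has already made it.

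**Conclusion.** The point holds in limited form. Section 7.2.3.4 defines a gestational-age percentile and then names, for about 94% of live births, a reference that it reads by age in the next bullet. As written, term births share one cut-off per sex and the reference switches at 37 weeks.

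The consequence is misclassification of a secondary endpoint in all three cohorts. Under the stated assumptions, about 20% to 27% of normally grown infants at week 37 and 2% to 4% at week 41 are called SGA instead of 10%. Bias between cohorts arises only if gestational length within term differs. With an assumed 10 to 20 point difference in births at 37 to 38 weeks, the spurious RR is about 1.10 to 1.31.

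The direction rests on one premise outside the text, that size rises with week within term; the sizes rest on all the assumed inputs. The primary endpoint and the arithmetic of Table 3 are unaffected. The definition should be corrected, but it does not threaten the study's main conclusion.

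**What to change.** In section 7.2.3.4, score SGA for all live births in the analysis, term and preterm, against a sex- and gestational-week-specific birth-size reference covering weight, length and head circumference. Take gestational age from the dating rule already in that section. Keep the NCHS pediatric curves for postnatal growth only. This also removes the change of reference at 37 weeks.

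The change is one sentence and needs no new data: sex, gestational age at pregnancy end and the three birth measurements are already collected (sections 7.2 and 7.2.3). The costs are some loss of comparability with any earlier studies that used the NCHS curves, and a check on Table 3. Section 8.4 draws its baseline rates partly from previous studies by the same group, so the 10% SGA baseline should be confirmed under the new reference.
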